#### **9.4.5 PHARMO, Netherlands**

The PHARMO Database Network, which is maintained by the PHARMO Institute for Drug Outcomes Research, is a population-based network of electronic health record databases that combines anonymous data from different primary and secondary healthcare settings in the Netherlands. These different data banks—including data from general practices, in- and outpatient pharmacies, clinical laboratories, hospitals, the cancer register, the pathology register, and the perinatal register—are linked on the patient level through validated algorithms. To ensure data privacy in the PHARMO Database Network, the collection, processing, linkage, and anonymisation of the data are performed by STIZON, which is an

independent, ISO/IEC 27001–certified foundation that acts as a trusted third party between the data sources and the PHARMO Institute. The PHARMO Institute is always seeking new opportunities to link with additional databanks and is currently exploring linkage with the COVID-19 immunisation register, which is collected by the Dutch National Institute for Public Health and the Environment (RIVM).

Currently, the PHARMO Database Network covers over 6 million active persons out of 17 million inhabitants of the Netherlands. Data collection period, catchment area, and overlap between data sources differ. Therefore, the final cohort size for any study will depend on the data sources included. All electronic patient records in the PHARMO Database Network include information on age, sex, socioeconomic status, and mortality. Other available information depends on the data source. The lag time of all databases is 1 year, except for the General Practitioner Database, which is updated every 3 months or less. A detailed description of the different data sources is given below ([Willame et al 2021](#)).

- The Hospitalisation Database includes discharge dates, discharge diagnoses, and procedures for hospitalisations longer than 24 hours (or shorter if the subject required a bed). Hospital discharge diagnoses are available from the Dutch National Basic Hospital Care Registration (Landelijke Basisregistratie Ziekenhuiszorg [LBZ]) and are recorded using ICD-10 codes. Procedures are coded according to the Dutch Hospital Data Foundation registration system.
- The General Practitioner Database comprises data from electronic patient records registered by GPs. The records include information on diagnoses and symptoms, laboratory test results, referrals to specialists, and healthcare product/drug prescriptions. Primary care data are available for a portion of the population of approximately 3.2 million inhabitants (approximately 20% of the Dutch population). Information on lifestyle variables (eg, BMI, smoking, alcohol consumption) is available in the General Practitioner Database if recorded by GPs in the electronic medical records.
- The Out-patient Pharmacy Database comprises GP- or specialist-prescribed healthcare products dispensed by the outpatient pharmacy. The dispensing records include information on type of product, date, strength, dosage regimen, quantity, route of administration, prescriber specialty, and costs. Drug dispensings are coded according to the World Health Organization (WHO) ATC classification system. Outpatient pharmacy data cover a catchment area representing 4.2 million residents (~25% of the Dutch population).
- The Netherlands Perinatal Registry is maintained by Perined and comprises data on pregnancies, births, and neonatal outcomes of births in the Netherlands, which are voluntarily collected by perinatal caregivers, mainly for benchmarking. For the current study, permission has been obtained from PHARMO as well as Perined to link the data with the PHARMO Database Network via the trusted third party and use the PHARMO Perinatal Research Network (PPRN). Records include information on mothers (eg, maternal age, obstetric history, parity), pregnancy (eg, mode of conception, mode of delivery), and children (eg, birth weight, gestational age, Apgar score). Diagnoses and symptoms are coded according to the Perinatal Registry code lists. Perinatal data are available with a lag time of 1 year.

## 9.5 Study Size

Across the proposed databases, the source population for the study includes approximately 33.8 million subjects (Table 4). All available data in each set will be used to identify subjects who received any COVID-19 vaccine.

**Table 4 Estimates of Study Size and Exposed Population, by Data Source**

Data source	Approximate current enrolled population (million, protocol V2.1)	Cumulative exposure estimate for the data source based on ECDC vaccine country distribution (doses, protocol V2.1) a	Actual exposure data (protocol V2.1)	Actual exposure data (Interim Report 2)
CPRD Aurum, UK b	13.4	4.9 million first doses and 1.8 million second doses	3.7 million patients who have had at least 1 dose (May 2021 database release)	4,301,194 (of these 3,938,490 were matched) (preliminary results from Interim Report 2)
VID (FISABIO), Valencia, Spain c	5	605,662	484,145 first doses and 171 second doses (communication 30 May 2021)	530,226 (of these, 517,015 were matched)
SIDIAP, Catalonia, Spain d	5.8	714,225	Number of exposures up to 02 Jun 2021 in Catalonia: 916,384 AZ doses	614,472 (of these, 609,842 were matched)
ARS Toscana, Italy e	3.6	411,719	197,267 first doses (communication 11 Apr 2021)	343,478 (of these, 336,889 were matched) (preliminary results from Interim Report 2)

**Table 4 Estimates of Study Size and Exposed Population, by Data Source**

Data source	Approximate current enrolled population (million, protocol V2.1)	Cumulative exposure estimate for the data source based on ECDC vaccine country distribution (doses, protocol V2.1) a	Actual exposure data (protocol V2.1)	Actual exposure data (Interim Report 2)
PHARMO, Netherlands f	3.5	426,725	34,000 first doses (20 May 2021) Based on GP data only; data from COVID-19 vaccination Information and Monitoring System (CIMS) may become available	175,149 (of these, 154,858 were matched)

a Number of doses for EU data sources were estimated using ECDC distribution data per country as of 24 May 2021, multiplied by the proportion of the national population covered in each database. This number also assumes that vaccine distribution in the country is uniform and that all distributed vaccines will be administered (<https://qap.ecdc.europa.eu/public/extensions/COVID-19/vaccine-tracker.html#distribution-tab>). For the CPRD Aurum, the estimates are based on vaccine distribution in the UK. See footnote b.

b The CPRD Aurum contains information on 13.4 million inhabitants in England and Northern Ireland, representing 20.4 % of the 65.8 million UK population. As of 12 May 2021, an estimated 23.9 million first doses and 9.0 million second doses of the AZ COVID-19 vaccine had been administered (<https://www.gov.uk/government/publications/coronavirus-covid-19-vaccine-adverse-reactions/coronavirus-vaccine-summary-of-yellow-card-reporting>).

c VID: 10.6% coverage among the 5,713,800 total AZ doses administered in Spain as of 21 May 2021, resulting in an estimated 605,662 doses captured in VID.

d SIDIAP: 12.5% coverage among the 5,713,800 total AZ doses administered in Spain as of 21 May 2021, resulting in an estimated 714,225 doses captured in SIDIAP.

e ARS Toscana: 6% coverage among the 6,861,980 total AZ doses administered in Italy as of 21 May 2021, resulting in an estimated 411,719 doses captured in ARS Toscana.

f PHARMO: 20.2% coverage among the 2,112,500 total AZ doses administered in the Netherlands as of 21 May 2021, resulting in an estimated 426,725 doses captured in PHARMO.

ARS Toscana, Regional Health Agency of Tuscany; AZ, AstraZeneca; CIMS, COVID-19 vaccination Information and Monitoring System (Netherlands); COVID-19, coronavirus disease 2019; CPRD, Clinical Practice Research Datalink; ECDC, European Centre for Disease Prevention and Control; EU, European Union; FISABIO, Foundation for the Promotion of Health and Biomedical Research of Valencia Region; GP, general practitioner; PHARMO, PHARMO Database Network of the PHARMO Institute for Drug Outcomes Research; SIDIAP, Information System for Research in Primary Care; UK, United Kingdom; VID, Valencia Health System Integrated Database.

The precision of study results was estimated for each comparator cohort: concurrent unvaccinated, active comparators, and historical comparators. Additionally, a power estimation for the SCRI design analysis was performed. All calculations assumed that the true IRR between the AZD1222-vaccinated cohort and each comparator cohort was 1.0. All the

calculations estimated the probability that the upper bound of the 95% confidence interval (CI) around the observed IRR was below 1.5, 2.0, 2.5, and 3.0 for various study sizes and AESI rates. The ratio between AZD1222 and comparator person-time varied depending on the type of comparator.

First, the precision of the estimates for the comparison of **AZD1222-vaccinated subjects with concurrent unvaccinated subjects** was estimated assuming a 3:1 ratio for the person-time of AZD1222-vaccinated subjects to concurrent unvaccinated subjects. In Interim Report 1, the follow-up of subjects in the concurrent unvaccinated cohort was short, leading to a 2:1 ratio of person-time despite a 1:5 matching ratio. Results from Interim Report 2 included a longer follow-up and almost the same number of subjects vaccinated with AZD1222, since AZD1222 was no longer administered. The results suggested that the actual ratio of person-time is likely to be 3:1 in the final analysis, with some variations across data sources. The anticipated precision of the study was estimated for one of the least frequent AESIs, Guillain-Barré syndrome (GBS), assuming a background rate of 2 events per 100,000 person-years, 84 days at risk (42 days per dose). With a study size of 5 million vaccinated subjects, it was anticipated that there was a 75% probability that the upper bound of the 95% CI around the observed IRR would be below 3.0 ([Table 5](#)).

The PRAC AR for Interim Report 1 (7 July 2022) requested that the MAH discuss the need for additional data sources. As per results from this Interim Report 1, 5.8 million subjects included in the study have received at least one dose of AZD1222. The number of AZD1222 vaccinees and data sources included in the current study at this time is considered acceptable for the purpose of interpreting findings as continuous measures that are estimated with varying degrees of precision ([Rothman and Greenland 2018](#)). Therefore, no additional data sources are considered necessary.

**Table 5 Probability That the Upper 95% Confidence Limit of the Observed IRR Will Be Below 1.5, 2, 2.5, and 3 for Various Study Sizes of Vaccinated Subjects, Assuming That the True RR is 1 and the Ratio of Vaccinated-to-Concurrent Unvaccinated Person-time is 3 to 1**

Adverse event (duration of risk interval after each dose)	Estimated background rate per 100,000 PY	People vaccinated	Upper confidence limit of IRR			
			1.5	2.0	2.5	3.0
Anaphylaxis (VAC4EU 2021, Willame et al 2021)	6	1,000,000	0.04	0.05	0.07	0.08
(3 days)	6	2,000,000	0.05	0.07	0.09	0.12
	6	3,000,000	0.05	0.09	0.12	0.16
	6	4,000,000	0.06	0.10	0.15	0.19
	6	5,000,000	0.07	0.12	0.17	0.23
GBS (VAC4EU 2021, Willame et al 2021)	2	1,000,000	0.06	0.11	0.16	0.22
(42 days)	2	2,000,000	0.09	0.18	0.28	0.38
	2	3,000,000	0.11	0.25	0.40	0.53
	2	4,000,000	0.14	0.32	0.50	0.65
	2	5,000,000	0.16	0.38	0.59	0.75
Bell's palsy (Morales et al 2013) (42 days)	38	1,000,000	0.47	0.90	0.99	1.00
VTE a (Heit 2015) (42 days)	100	1,000,000	0.87	1.00	1.00	1.00

a This adverse event is a constituent of the composite AESI “thrombosis.”

Note: Calculations assume a true IRR of 1.0 and a ratio of 1-to-4 exposed to unexposed person-years. Calculations also assume that each person contributes 6 days of follow-up for anaphylaxis (3-day risk interval x 2 doses), 56 days for stroke (28-day risk interval x 2 doses), and 84 days (42-day risk interval x 2 doses) for all other adverse events (Rothman and Greenland 2018). Calculations follow the method of Rothman and Greenland (2018).

AESI, adverse event of special interest; GBS, Guillain-Barré syndrome; IRR, incidence rate ratio; PY, person-years; RR, risk ratio; VAC4EU, Vaccine monitoring Collaboration for Europe; VTE, venous thromboembolism.

Second, the precision for the results comparing **AZD1222-vaccinated subjects with active comparators and historical comparators** was estimated. The estimation of the precision of the results assumed a 1:1 ratio for the person-time of AZD1222-vaccinated subjects to active comparators and to historical controls (Kaura et al 2022). For one of the rarest anticipated events, GBS, assuming a background rate of 2 events per 100,000 person-years, 84 days at risk (42 days per dose), and a study size of 5 million vaccinated subjects, it was anticipated that there was a 96% probability that the upper bound of the 95% CI around the observed IRR would be below 3.0 (Table 6).

The number of AZD1222 vaccinees and data sources for the comparison of AZD1222 vaccinees with active and historical comparators is considered acceptable for the purpose of

interpreting findings as continuous measures that are estimated with varying degrees of precision. Assuming 1:1 ratio of matching will be achieved with the 5.8 million AZD1222 vaccinated subjects, no additional data sources are considered necessary.

**Table 6 Probability That the Upper 95% Confidence Limit of the Observed IRR Will Be Below 1.5, 2, 2.5, and 3 for Various Study Sizes of Vaccinated Subjects, Assuming That the True RR is 1 and the Ratio of Vaccinated Subjects to Active Comparators Person-time and to Historical Comparators Person-time is 1 to 1**

Adverse event (duration of risk interval after each dose)	Estimated background rate per 100,000 PY	People vaccinated	Upper confidence limit of IRR			
			1.5	2.0	2.5	3.0
Anaphylaxis (VAC4EU 2021, Willame et al 2021)	6	1,000,000	0.05	0.07	0.09	0.12
(3 days)	6	2,000,000	0.06	0.10	0.15	0.19
	6	3,000,000	0.07	0.13	0.20	0.27
	6	4,000,000	0.08	0.16	0.25	0.34
	6	5,000,000	0.09	0.19	0.30	0.41
GBS (VAC4EU 2021, Willame et al 2021)	2	1,000,000	0.09	0.18	0.28	0.38
(42 days)	2	2,000,000	0.14	0.32	0.50	0.65
	2	3,000,000	0.19	0.44	0.67	0.82
	2	4,000,000	0.23	0.56	0.79	0.92
	2	5,000,000	0.28	0.65	0.87	0.96
Bell's palsy (Morales et al 2013) (42 days)	38	1,000,000	0.76	1.00	1.00	1.00
VTE a (Heit 2015) (42 days)	100	1,000,000	0.99	1.00	1.00	1.00

a This adverse event is a constituent of the composite AESI “thrombosis.”

Note: Calculations assume a true IRR of 1.0 and a ratio of 1-to-1 exposed to unexposed PY. Calculations also assume that each person contributes 6 days of follow-up for anaphylaxis (3-day risk interval x 2 doses), 56 days for stroke (28-day risk interval x 2 doses), and 84 days (42-day risk interval x 2 doses) for all other adverse events. Calculations follow the method of Rothman and Greenland (2018).

AESI, adverse event of special interest; GBS, Guillain-Barré syndrome; IRR, incidence rate ratio; PY, person-years; RR, risk ratio; VAC4EU, Vaccine monitoring Collaboration for Europe; VTE, venous thromboembolism.

Third, for the outcome of TTS, study size implications were evaluated in terms of precision of the absolute risk difference, rather than IRR, because the background risk for this newly described syndrome is unknown and conceivably could be zero (Table 7). Relative risks cannot be quantified when the risk in the reference group is zero. Moreover, effect measures in terms of absolute risk are preferred to relative risk to assess the public health impact of a safety concern and how it may factor into benefit-risk balance. Among vaccinated individuals,

the risk has been estimated from reporting rates, which have ranged between 1 per 100,000 and 1 per 250,000 per vaccinee (WHO 2021). The duration of the risk period for TTS is not known, but for this exercise, it has been assumed to be 4 weeks; based on case reports published by 11 May 2021, the onset of this outcome appears to occur within 4 weeks of vaccination (Greinacher et al 2021, Scully et al 2021). Table 7 shows the probability that the upper 95% confidence limit of the absolute risk difference for TTS will fall below various thresholds, across a range of different study sizes, assuming a 1-to-1 ratio of vaccinated to unvaccinated subjects. For example, assuming that the true 4-week risk of TTS is 1 per 100,000 vaccinees and that the background risk is zero, with 1,000,000 people vaccinated there is a 99% probability that the upper confidence limit of the absolute risk difference will fall below 3.0 per 100,000.

**Table 7 Probability That the Upper 95% Confidence Limit of the Observed 4-Week Absolute Risk Difference for TTS Will Be Below Various Thresholds for Different Study Sizes, Assuming that a True 4-Week Risk Among Vaccinees is 1 per 100,000 or 1 per 250,000**

Estimated 4-week incidence among vaccinated individuals	Estimated 4-week incidence among concurrent unvaccinated individuals	People vaccinated	Upper confidence limit of ARD (per 100,000)			
			1.5	2.0	2.5	3
1 per 100,000	0	1,000,000	0.35	0.89	> 0.99	> 0.99
		2,000,000	0.61	0.99	> 0.99	> 0.99
		3,000,000	0.78	> 0.99	> 0.99	> 0.99
		4,000,000	0.89	> 0.99	> 0.99	> 0.99
		5,000,000	0.94	1.00	1.00	1.00
			Upper confidence limit of ARD (per 250,000)			
			1.5	2.0	2.5	3
1 per 250,000	0	1,000,000	0.17	0.52	0.85	0.98
		2,000,000	0.29	0.81	0.99	> 0.99
		3,000,000	0.41	0.93	> 0.99	> 0.99
		4,000,000	0.52	0.98	> 0.99	> 0.99
		5,000,000	0.61	0.99	> 0.99	> 0.99

Note: The actual incidence of TTS is not known; estimates here are based on reporting rates among vaccinated subjects (WHO 2021). The actual background incidence of TTS is also unknown. Calculations presented here assume a 1-to-1 ratio of vaccinated to unvaccinated subjects and follow the methods described in Rothman and Greenland (2018).

[figure not shown]
ARD, absolute risk difference; TTS, thrombosis with thrombocytopenia syndrome; WHO, World Health Organization.

Finally, the study size was estimated for the SCRI study component. The methods described by Musonda et al (2006) were used. These methods follow a traditional power and statistical

significance approach and do not currently allow a precision approach. The 2 parameters of most interest and specific to the SCRI design are the proportion of the observation period in the exposed state (ie, 50% in this study) and the relative incidence of events during the observation period in the exposed state compared with the incidence of events during the observation period in the unexposed state (ie, IRR). For this estimation, we assumed several IRR scenarios of 1.5, 2, 3 and 4. The study size estimation is not based on independent subjects but rather on the occurrences of the event of interest, which may happen more than once in the same subject. The SCRI includes only subjects that experienced the event of interest at least once.

Figure 7 displays different scenarios of IRRs for AESIs assuming a 50% of observation period in the exposed state, an alpha error of 5%, and a range of 0 to 200 events. In scenarios with an IRR of 1.5, including 200 events, a maximum power of 80% will be expected. In the scenario considering an IRR of 2 for certain AESIs, approximately 70 events will be required to have a power of 80%. Finally, in scenarios considering an IRR of 3 with 40 events or an IRR of 4 with 20 events, the study will have more than 90% power.

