### 9.1.1 Retrospective Cohort Design

A retrospective cohort of exposed subjects will be selected. Subjects will enter the exposed cohort upon their first vaccination with AZD1222. Subjects in the AZD1222 cohort will be matched, as applicable, to 3 different comparator cohorts: concurrent unvaccinated subjects, active comparators (ie, subjects vaccinated with an mRNA vaccine against COVID-19), and historical comparators enrolled in the study data sources during the pre-pandemic period (ie, from 2017 to 2018). The AZD1222 cohort will be matched, as applicable, independently to the 3 different comparator cohorts on calendar date of vaccination, age, sex, region, prior COVID-19, and status according to each of the 5 special populations (Section 9.2.1.2). Propensity scores (PSs) will be used to address confounding, balancing multiple covariates such as comorbidities, markers of healthcare utilisation and comedication between the vaccinated and the different comparator cohorts (Austin 2014, Webster-Clark et al 2021). Relative risk will be the main measure of effect, which will be estimated using incidence rate ratios (IRRs), prevalence proportion ratios (PPRs), or hazard ratios (HRs), depending on the analysis and outcome. Absolute risk difference measures will include incidence rate differences, prevalence proportion differences (PPD), and  $1 - KM^2$  differences.

In the cohort study, the initial plan was to use concurrent, rather than historical, comparator (unvaccinated) subjects because they are at risk for COVID-19, and COVID-19 may function as an important covariable in the analyses of several of the safety endpoints. Moreover, both healthcare-seeking behaviours and healthcare delivery during the pandemic differ from those during the pre-pandemic era. The potential challenge with this approach is that during the pandemic, concurrent unvaccinated subjects in the comparator group may themselves become vaccinated over time. Results from Interim Reports 1 and 2 confirmed that the duration of follow-up among concurrent unvaccinated subjects was short (median, < 2 months in all data sources) and probably not long enough to evaluate AESIs with unknown risk window—(those with a risk window that ends at 180 or 365 days). Thus, additional comparators for whom the follow-up is expected to be longer were requested by the PRAC and have been added to the

---

[figure not shown]
 KM, Kaplan-Meier estimate.

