#### Concurrent Unvaccinated Comparators Cohort

A potential comparator subject (**concurrent unvaccinated comparators**) will be eligible to be matched from the date the subject meets *all* the following inclusion criteria:

- Has at least 12 months of prior data available.
- Has not received any COVID-19 vaccine, including AZD1222.

The **index date** for the unvaccinated subjects will be assigned as the index date of the matched vaccinated subject.

Unexposed subjects that are eligible at the index date of an exposed subject with the same age ( $\pm 2$  years), sex, prior diagnosis of COVID-19, and status according the 5 special populations will be **matched** to the exposed subject. Matching will be done with replacement in a ratio of 1 vaccinated to 1 unvaccinated subject.

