#### 9.2.3.1 Cohort Design: Follow-up

Follow-up will start on the index date and end on the earliest of the following possible follow-up termination dates:

- The end date of the study period.
- The subject's enrolment termination date in the health plan or system.
- The subject's date of death.
- For the specific evaluation of each AESI:
  - The date of the first diagnosis of a specific AESI recorded after the index date, during the study period. For composite outcomes, follow-up will be censored at the date of the first occurrence of any of the components.
  - For the evaluation of AESIs with **known risk windows** (ie, those for which the end of the risk window is other than 180 or 365 days), the date on which the defined risk window for the last dose ends (the last dose was dose 1 if only 1 dose was received and dose 2 if 2 or more doses were received).
    - For subjects who received 2 doses of AZD1222, or of an mRNA vaccine, and were not censored due to an AESI or other censoring criteria before the second dose, a second risk window will follow the second dose; and for concurrent unvaccinated comparators or historical comparator subjects, a corresponding second risk interval will also apply, mirroring the timing of the second risk interval for the matched vaccinee (Figure 4). As previously noted, the start and duration of the risk windows will be specific to each outcome, corresponding to the period when the biologic effect of a vaccine is hypothesised to increase the risk for the particular AESI (Section 9.1.2). If an AESI occurs during a gap between doses, this AESI will not be included as an event in the study, and as stated above, the follow-up will be censored at the time of the AESI.
    - This risk window applies to both the vaccinee and matched comparator subjects.

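### Table 5 applies one 3:1 person-time ratio to every AESI; for anaphylaxis the matched design allows at most about 2:1 in practice, and for the 42-day AESIs the ratio is not shown to hold inside the risk windows

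*Protocol*

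**What the plan says.** Section 9.5 sets the precision of the concurrent-unvaccinated comparison "assuming a 3:1 ratio for the person-time of AZD1222-vaccinated subjects to concurrent unvaccinated subjects". It reports that Interim Report 1 had short comparator follow-up, "leading to a 2:1 ratio of person-time despite a 1:5 matching ratio", and then says of Interim Report 2: "The results suggested that the actual ratio of person-time is likely to be 3:1 in the final analysis, with some variations across data sources". It does not say whether that person-time is whole follow-up or time inside risk windows.

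The design rules that fix the person-time are elsewhere in the protocol:

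- Section 9.2.1.1.3: the comparator takes the matched vaccinee's index date, and "Matching will be done with replacement in a ratio of 1 vaccinated to 1 unvaccinated subject".
- Section 9.2.3.1: when the vaccinee has a second dose, "a corresponding second risk interval will also apply, mirroring the timing of the second risk interval for the matched vaccinee".
- Table 5 note: "each person contributes 6 days of follow-up for anaphylaxis (3-day risk interval x 2 doses"; the 42-day AESIs have 84 days each.
- Section 9.1.1: "the duration of follow-up among concurrent unvaccinated subjects was short (median, < 2 months in all data sources".
- Sections 9.7.6 and 9.7.7: anaphylaxis is analysed by prevalence proportions, with their ratios and differences, not by rates.

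The title of Table 5 gives 3 to 1, but its note reads: "Calculations assume a true IRR of 1.0 and a ratio of 1-to-4 exposed to unexposed person-years".

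**The concern.** For an AESI with a known risk window, only days inside the windows count. A vaccinee and a 1:1 matched comparator start their first window on the same day and have the same window length. Their person-time can differ only when the comparator is censored inside a window or before the second one. How far apart they drift therefore depends on window length: very little for 3 days, possibly a lot for 42 days. A single ratio for both is hard to defend, and follow-up beyond the windows has no bearing on either.

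The affected figures are the anaphylaxis rows, the 75% statement for GBS in Section 9.5 and the 90% statement for Bell's palsy in the abstract. All describe the primary comparison. Beside the 1:1 figures in Table 6, they may make it look weaker against the exploratory comparisons than it is.

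**Working it through.** **Reproducing Table 5.** The table's figures follow from P = Φ(ln U / SE − 1.96), with SE = √(1/a + 1/b), a = rate × N × days/365.25 and b = a/ratio, for a true IRR of 1.

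| Row | a | b at 3:1 | SE | P | Stated |
|---|---|---|---|---|---|
| GBS, 2 per 100,000 PY, 5 million, 84 days, U = 3 | 23.0 | 7.67 | 0.417 | 0.750 | 0.75 |
| Anaphylaxis, 6 per 100,000 PY, 5 million, 6 days, U = 3 | 4.93 | 1.64 | 0.901 | 0.229 | 0.23 |
| Bell's palsy, 38 per 100,000 PY, 1 million, 84 days, U = 2 | 87.4 | 29.1 | 0.214 | 0.900 | 0.90 |

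The cells checked across the table agree at 3:1 to within 0.005. The note's ratio (four times as much unexposed as exposed person-time) does not give the table: GBS would have b = 92.0 and P = 0.997.

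**Anaphylaxis: what ratio can the design give?** The vaccinee with two doses contributes 3 + 3 = 6 days.

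- If every comparator completes the first 3 days and none reaches the second window, the ratio is 6/3 = 2:1.
- A ratio of 3:1 needs a mean of 6/3 = 2 comparator days, so a third of first-window comparator time must be lost within 3 days of matching. Under exponential dropout this means a median follow-up of about 2.4 days.
- With exponential medians of 30 to 60 days and dose 2 at day 28 to 84 (the interval in Section 7), the ratio is about 1.2 to 1.8:1.

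**42-day AESIs.** With rate λ = ln 2 / median and non-overlapping windows, expected comparator days are [(1 − e^(−42λ))/λ] × (1 + e^(−gλ)), where g is the dose interval. The vaccinee has 84 days. With dose 2 at day 28 the windows overlap, so both members are counted over the joined 70 days. All vaccinees are taken to receive dose 2.

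| Median comparator follow-up | Ratio, dose 2 at day 28 | Ratio, dose 2 at day 84 |
|---|---|---|
| 20 days | 2.66 | 3.60 |
| 30 days | 2.02 | 2.73 |
| 59 days | 1.47 | 1.85 |

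The ratio equals 3:1 at a median of about 17 days (dose 2 at day 28) to 26 days (day 84).

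Without the exponential assumption 3:1 is not excluded at longer medians. If the median lies between 42 and 60 days, at least half of comparators complete the first window. That guarantees only 0.5 × 42 = 21 comparator days, and 84/21 = 4:1.

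**Effect on the stated probabilities.**

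| Ratio | GBS, 5 million, < 3.0 | Anaphylaxis, 5 million, < 3.0 | Bell's palsy, 1 million, < 2.0 |
|---|---|---|---|
| 3:1 | 0.75 | 0.23 | 0.90 |
| 2.7:1 | 0.78 | 0.24 | 0.92 |
| 2:1 | 0.86 | 0.29 | 0.96 |
| 1.5:1 | 0.92 | 0.34 | 0.98 |
| 1:1 | 0.96 | 0.41 | > 0.99 |

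For anaphylaxis only the rows at 2:1 and below are realistic.

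**The case against.** The strongest reply is that Table 5 contains no miscalculation and that 3:1 comes from the study's own interim data. Both points stand. A reader might infer that the table's arithmetic is wrong; it is not, since the figures reproduce at the stated ratio. The question is whether that ratio belongs to the planned analysis.

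A reader might also infer that 3:1 is impossible or unlikely for the 42-day AESIs. The protocol does not support that. It gives only an upper bound on median comparator follow-up, and medians of roughly 17 to 26 days produce 3:1. The 30-to-60-day range and the exponential form used above are assumptions. Nor can it be shown that 3:1 is a whole-follow-up ratio. Section 9.5 mentions it next to longer follow-up, which points that way, but does not say so. Interim Report 1's 2:1 under 1:5 matching is about 10:1 per matched comparator; inside 3-day windows that would mean 6/10 = 0.6 comparator days, so it can hardly be an in-window figure for anaphylaxis. It does not settle what the Interim Report 2 figure measures.

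For anaphylaxis, one can fairly add that precision is poor at any of these ratios, that Section 9.9.2 already warns of this, and that a corrected person-time ratio would still be the wrong quantity for a prevalence proportion. The last point shapes the fix; none of them supports 3:1 for that row.

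**Conclusion.** The point holds firmly for anaphylaxis. Under 1:1 matching with mirrored 3-day windows, 3:1 would require implausibly fast loss of comparators. The stated 0.23 is too low, with 0.29 at the practical ceiling of 2:1 and 0.41 at 1:1. This assumes that nearly all comparators complete the first 3 days.

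For the 42-day AESIs the finding is narrower: the protocol does not show that 3:1 holds inside the windows. If median comparator follow-up is 30 to 60 days with exponential dropout and all vaccinees receive dose 2, the ratio is about 1.5 to 2.7:1. GBS would then be about 0.78 to 0.92 instead of 0.75, and Bell's palsy about 0.92 to 0.98 instead of 0.90.

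It might be inferred that the decision against further data sources rests on unsound figures. It is not undermined: at each of these lower ratios the probabilities rise, so Table 5 errs on the conservative side. The 1-to-4 ratio in the note is a plain contradiction of the title and text, whatever the interim data show.

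**What to change.** 1. Restate the anaphylaxis rows on the prevalence-proportion scale, using the matched persons at risk in each dose window.
2. State which person-time the Interim Report 2 ratio describes. Recompute the 42-day rows, the 75% GBS statement in Section 9.5 and the 90% Bell's palsy statement in the abstract with the ratio observed inside those windows. Keep 3:1 only if it is confirmed there.
3. Correct the ratio in the Table 5 note to the one actually used.

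The cost is a recalculation from interim data already held and a few text edits. Study conduct does not change.
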